9. ADVERSE EVENT RECORDING AND REPORTING

9.1 Recording Requirements

Research subjects will be routinely questioned about adverse events at study follow-up visits.

➤ RECORDING REQUIREMENT

All observed or volunteered adverse events (serious or non-serious) and abnormal test findings, regardless of suspected causal relationship to the study device will be recorded in the subjects' case histories (source data, case report form). For all adverse events, sufficient information will be obtained to permit 1) an adequate determination of the outcome of the event (i.e., whether the event should be classified as a serious adverse event) and; 2) an assessment of the casual relationship between the adverse event and the ~~ABI24 system~~.

Adverse events or abnormal test findings felt to be associated with the ~~ABI24 system~~ will be followed until the event (or its sequel) or the abnormal test finding resolves or stabilizes at a level acceptable to the Sponsor-Investigator.

➤ ABNORMAL TEST FINDINGS

An abnormal test finding will be classified as an adverse event if one or more of the following criteria are met:

- The test finding is accompanied by clinical symptoms
- The test finding necessitates additional diagnostic evaluation(s) or medical/surgical intervention; including significant additional concomitant drug treatment or other therapy
- The test finding leads to discontinuation of subject participation in the clinical research study
- The test finding is considered an adverse event by the Sponsor-Investigator of the IND or IDE application
- Of note, simply repeating a test finding, in the absence of any of the other listed criteria, does not constitute an adverse event.

➤ **CASUALTY AND SEVERITY ASSESMENT**

The Sponsor-Investigator of the IND or IDE application will promptly review documented adverse events and abnormal test findings to determine 1) if the abnormal test finding should be classified as an adverse event; 2) if there is a reasonable possibility that the adverse event was caused by the ABI24-system541; and 3) if the adverse event meets the criteria for a serious adverse event.

If the Sponsor-Investigator's final determination of causality is "unknown and of questionable relationship to the study device", the adverse event will be classified as associated with the use of the ABI24-system541-for reporting purposes. If the Sponsor-Investigator's final determination of causality is "unknown but not related to the study device," this determination and the rationale for the determination will be documented in the respective subject's case history (case report form).

9.2 REPORTING PROCEDURES

➤ **REPORTING OF ADVERSE REACTIONS TO FDA**

- Written IND Safety Reports (if applicable)
- Telephoned IND Safety Reports - Fatal or life-threatening suspected adverse reactions

➤ **Reporting Adverse Events to Other External Entities**

Adverse event reports will also be submitted to the Cochlear Americas, which has provided a Right of Reference Letter for the Nucleus ABI24-system541, in accordance with their respective reporting guidelines.

➤ **Reporting Adverse Events to the Human Studies Committee (Please follow HSC Policy "REPORTING ADVERSE EVENTS AND UNANTICIPATED PROBLEMS")**

1. Reporting of Unexpected and Related/Possibly Related Events

Serious Adverse Event (SAE)

Any serious adverse event will be reported to the HSC. These SAE include those that both (i) are unexpected and related/possibly related to research; and (ii) occur while the subject is enrolled in the study or that occur within 30 days of the conclusion of the subject's participation in the study, of which the PI or study staff become aware. In order to determine whether a specific adverse event is unexpected, the PI will consider whether the event is consistent with the risks described in the protocol-related documents (e.g. protocol, consent form, Investigator's Brochure). In order to determine whether a specific adverse event is related or possibly related to subject's participation in the research, the PI will consider the temporal relationship between the event and the investigational product being studied or study procedure. If an adverse event is at least partially caused by the procedures and /or investigational products, it will be considered related/possibly related to research.

Any adverse events that are serious, unexpected and related or possibly related to the study will be reported to the HSC within 7 calendar days from the time the PI becomes aware of the event. Any unexpected and study-related death will be reported to HSC within 24 hours of the PI's knowledge of the event by e-mail or telephone. A completed AE report form will be submitted to HSC within 7 calendar days of initial HSC notification. If the PI becomes aware more than 30 days after the conclusion of a subject's participation of a serious adverse event that is both related to the research and unexpected, the PI will report the event to HSC at the time he/she becomes aware of it.

Non-Serious Adverse Event

All non-serious adverse events that are unexpected and related or possibly related to the research will be reported to the HSC within 30 calendar days from the time the PI becomes aware of the event.

2. Reporting of Expected and Related/Possibly Related Events

The PI will submit a summary report to the HSC for all serious and non-serious events that are expected and related/possibly related to the study at the time of continuing review.

3. Reporting of Unanticipated Problems

The PI will promptly report to the HSC Unanticipated Problems (UAPs) involving risks to subjects or others. In order to determine whether a specific problem constitutes a UAP, the PI will consider the following:

- The vast majority of adverse events occurring in human subjects do not represent UAP because most AEs are expected in the context of known toxicities or side effects of the research procedures and/or are due to the natural history of subjects' underlying diseases and conditions;
- a small proportion of AEs do represent UAPs; and
- UAPs may include events that are not adverse events.

All UAPs involving risks to subjects or others will be reported in writing to the HSC within 7 calendar days from the time the PI becomes aware of the event. If a UAP or an unexpected SAE results in a subject's death or was potentially life-threatening, the PI will notify HSC through e-mail or phone within 24 hours from the time the event is identified. A follow-up report will be submitted at a later date when more information is available. The PI will notify HSC through e-mail or phone within 24 hours from the time the event is identified for UAPs that take the form of a data loss.

9.3 Withdrawal of Subjects due to Adverse Events

Subjects experiencing major adverse events will be referred for appropriate care as needed. The severity of adverse events will be determined by the investigator in consultation with the HSC. Briefly, events that lead to irreversible or permanent disability of the patient will be considered serious and the subject will be reminded that participation in the study is voluntary and that withdrawal is possible at any time. If the subject remains interested in continuing to participate in the study, then after receiving the appropriate care, data will continue to be collected from the subject at follow-up visits as described in the study design. Medical attention and follow-up for any adverse events will continue until the adverse health concern has resolved or if not, then continued indefinitely. If a subject is withdrawn from the study due to an adverse event, they will be replaced by recruiting a new study participant from clinic.

10. STATISTICAL METHODS/DATA ANALYSIS

10.1 Primary endpoint(s) or outcome measure (s)

The study has a primary endpoint of five years following ABI surgery for up to fifteen study participants. Outcomes measures include audiologic measures and subjective questionnaires as described in previous sections, as well as safety assessments completed throughout the study.

Our previous work has established the importance of these physiological, psychophysical, speech tests, questionnaires on efficacy, and safety measures as a comprehensive method for assessing the outcomes of ABI surgery in non-NF2 patients. In particular, using these measures we can obtain both objective and subjective data to assess the safety and efficacy of ABI placement in non-NF2 patients and thereby understand how ABI placement has influenced patients' hearing and quality of life. In addition, by comparing our findings and measures to data obtained in other patient populations such as NF2 patients, we will better understand whether ABI placement in non-NF2 patients has improved safety and efficacy compared to ABIs in other patient populations.

10.2 Secondary endpoints or outcome measure (s)

There are no secondary endpoints or outcome measures for this study.

10.3 Sample Size Determination

Our study will recruit fifteen participants for placement of a Nucleus ABI24 system541 device with follow-up measurements and assessments for five years post-operatively. Although our study is limited to a small sample size of up to fifteen patients, the single subject research design will allow each subject to serve as his or her own control, accommodating heterogeneity of the subjects' backgrounds and providing adequate power to test the major hypotheses. Previous studies have used a similar study design and sample size, with statistically significant findings regarding efficacy and safety of ABIs in non-NF2 patients.

10.4 Analysis Population (if applicable)

Given the small sample size of up to fifteen patient for our study, we will plan to analyze data obtained from all participants. If a subject withdraws from the study, data obtained from their participation in the study will still be incorporated into outcomes and safety analyses.

10.5 Effectiveness Analysis (if applicable)

As this study is a single-subject research design, Nucleus ABI24 system541 effectiveness results will be analyzed for each subject individually. The data will be described using conventional descriptive statistics. Data analyses will be conducted using appropriate non-parametric statistical tests. When CI performance data from the same ear are available in a subject or can be obtained prior to ABI placement, comparisons with subsequent ABI performance will be generated. In addition, outcomes from non-NF2 patients enrolled in the current study will be compared to data collected in previous outcomes of the Nucleus ABI24 in NF2 patients using standard statistical tests. For all statistical analyses, a $p \leq 0.05$ level of significance

will be used. Any subsequent deviations from the statistical plan will be described and justified in a protocol amendment and/or in the final report submitted to this application.

10.6 Safety Analysis

As this study is a single-subject research design, Nucleus ABI24-system541 safety results will be analyzed for each subject individually. The data will be described using conventional descriptive statistics. Data analyses will be conducted using appropriate non-parametric statistical tests. Safety outcomes from non-NF2 patients enrolled in the current study will be compared to data collected in previous analyses of the Nucleus ABI24-system541 in NF2 patients using standard statistical tests. For all statistical analyses, a $p \leq 0.05$ level of significance will be used. Any subsequent deviations from the statistical plan will be described and justified in a protocol amendment and/or in the final report submitted to this application.

10.7 Interim Analysis

Interim analysis will be completed once three, five, and eight patients are enrolled. These analyses will be completed at one and three years post-operatively for each of these cohorts. Interim analysis will be performed by study staff and the Investigator and results will be shared with the HSC through routine study renewal forms. If significant concerns arise regarding safety of the proposed device, these analyses will be shared with the HSC within 7 days and appropriate discussion to follow. Of note, the safety concerns described here do not include adverse or unanticipated safety events, which will be handled as described in Section 9.

10.8 Data and Safety Monitoring

All persons working on the study will be briefed by the investigator or other leaders of the trial regarding their role in the study and appropriate data management and safety monitoring procedures. During these meetings, the ABI device as well as individual trial-related duties and functions will be discussed. The investigator or other leaders of the study will provide an opportunity for all persons assisting with the

trial to ask questions and clarify the protocol and their individual role. Each individual will be required to read the study protocol and acknowledge that they have read and understand the protocol along with their trial related duties and functions.

The investigator and study staff will monitor the validity and integrity of the data and any safety concerns as well as adherence to the IRB-approved protocol through regular biweekly or monthly meetings in which collected data is shared, new analyses are discussed, and any issues with protocol adherence are reviewed.

A research assistant will be responsible for monitoring the study, including obtaining source documents, organizing completed informed consent forms, reviewing the accuracy and completeness of case report forms, and managing the protocol timeline to ensure that all assessments are appropriately administered and collected from study participants.

12. DATA HANDLING AND RECORD-KEEPING

12.1 Data Recording and Record-Keeping

A Case Report Form (CRF) will be completed for each subject enrolled into the clinical study. The Sponsor-Investigator will review, approve and sign/date each completed CRF; the Sponsor-Investigator's signature serving as attestation of the Sponsor-Investigator's responsibility for ensuring that all clinical and laboratory data entered on the CRF are complete, accurate and authentic.

Clinical data that may be recorded directly on the CRF include: subjective report of symptoms, audiologic measures, lab values, and physical exam findings. Any missed, unused, or spurious data will be reviewed by the Investigator and followed up by study personnel. Subject specific data and Case Report Forms will be coded with a numeric random identifier, with information regarding which codes correspond to which

subjects stored on secure information systems at Mass. Eye and Ear. Electronic systems used are in compliance with FDA electronic records and signature regulations.

14. STUDY DISCONTINUATION CRITERIA

14.1 Discontinuation of Individual Research Subjects

As described, safety measures will include complications questionnaires and frequent post-operative follow-up visits. Inquiries about both major and minor complications will be made and any complications will be recorded. A research assistant will regularly review safety measures every month for all study participants and discuss any safety concerns/adverse outcomes with the investigator. The investigator will then decide whether the research study should be altered or stopped. If a clear answer is not evident, the investigator will discuss the safety concern with the Human Studies Committee and make appropriate adjustments to the study as needed. Other discontinuation criteria are described under Section 5.2 (Withdrawal of subjects due to non-compliance/adherence) and section 9.3 (Withdrawal of subjects due to adverse events) of the clinical protocol.

If withdrawn subjects are agreeable to measurements of clinical outcomes and assessments of device safety, these data will be collected until five years following ABI surgery. As with other criteria for withdrawal, subjects that are withdrawn will be replaced through recruitment of additional study participants in clinic.

14.2 Sponsor-Investigator Discontinuation of the Clinical Research Study

At this time, the sponsor-investigator has no known criteria for discontinuation of the clinical research study. Any protocol modifications will be submitted prospectively to the HSC and to the FDA for discontinuation of parts of the clinical study. If portions of the study must be discontinued, the HSC and the FDA will be notified promptly of discontinuation, including which portions of the study (if any) remain. In addition, enrolled subjects will be notified at follow-up appointments or by phone of discontinuation of any aspects of the study. If parts of the clinical study are

discontinued, a revised informed consent will be discussed and obtained from subjects for continued participation in the study. All study staff and sub-investigators will be notified directly by the investigator of discontinuation of parts or all of the clinical research study. Because all audiologic measurements and safety assessments in this study are part of normal routine follow-up after ABI surgery, these measures will continue to be obtained following discontinuation of the study through normally scheduled follow-up appointments. However, subjective questionnaires will not be administered to subjects following discontinuation of the study.

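### Section 14.2 states no criteria for stopping the study, and nothing in the supplied text pauses implantation for ethics committee review after a related death or permanent disability

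*Combined protocol and SAP*

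**What the plan says.** - **Stopping the study.** Section 14.2: "At this time, the sponsor-investigator has no known criteria for discontinuation of the clinical research study". The rest of 14.2 covers notification, renewed consent and continued measurement.
- **Who decides.** Section 14.1, after the monthly safety review: "The investigator will then decide whether the research study should be altered or stopped". The HSC comes in conditionally: "If a clear answer is not evident, the investigator will discuss the safety concern with the Human Studies Committee".
- **HSC reporting.** Section 9.2 opens by saying that any serious adverse event is reported to the HSC, then describes these as events that are unexpected and related or possibly related. Such events have 7 calendar days, and an unexpected study-related death has 24 hours. For unanticipated problems: "All UAPs involving risks to subjects or others will be reported in writing to the HSC within 7 calendar days". Related events judged expected go in a summary report, "for all serious and non-serious events that are expected and related/possibly related to the study at the time of continuing review".
- **FDA and manufacturer.** Section 9.2 also lists reports to the FDA, including telephoned reports of fatal or life-threatening suspected reactions, and reports to the manufacturer.
- **Severity.** Section 9.3: "The severity of adverse events will be determined by the investigator in consultation with the HSC". It classes permanent disability as serious and lets the subject choose whether to continue.
- **Interim analyses.** Section 10.7 sends device safety concerns to the HSC within 7 days, but refers adverse events back to section 9.
- **Replacement.** Section 9.3: "If a subject is withdrawn from the study due to an adverse event, they will be replaced by recruiting a new study participant from clinic". Sections 5.2, 7.7 and 14.1 also provide for replacement, and none makes it conditional on a review.

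**The concern.** The operation places an electrode array on the brainstem and cannot be undone for a subject who has already had it. HSC review of a related death or permanent disability can therefore protect only subjects not yet implanted, and its value depends on whether it comes before or after the next operation. If it comes after, any change it makes to technique, selection or the risk wording in the consent form is too late for that subject.

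The plan sets times for telling the HSC about some events, but no point at which implantation waits for an answer. The sponsor-investigator determines causality and seriousness under 9.1, and under 14.1 also decides whether to continue.

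**Working it through.** **Text check.** For each provision, does it hold the next implantation until an outside body has reviewed the event?

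| Section | What it provides | A hold? |
|---|---|---|
| 9.2 | HSC reports at 24 hours, 7 days or continuing review; FDA and manufacturer reports | No |
| 9.3 | HSC consulted on severity, no time stated | No |
| 10.7 | Interim safety concerns to the HSC within 7 days; adverse events left to section 9 | No |
| 10.8 | Monitoring by the investigator and study staff | No |
| 14.1 | Investigator may alter or stop; HSC if the answer is unclear | Discretion only |
| 14.2 | No criteria | No |

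**Size.** There is no safety figure in the plan to reproduce. From the documents: up to 15 subjects, with a goal of 10 (section 3.1). I take 15 as the total implanted. Assumed: per-subject risk q of a triggering event of 1%, 2% or 5%; accrual of 3, 5 or 8 per year; a continuing-review interval of 6 or 12 months; an HSC review of 2 to 8 weeks.

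1. Chance of at least one event among N is 1 − (1 − q)^N. For example, 1 − 0.99^15 = 0.140.
2. Mean number still to be implanted at the first event, given at least one among 15, is 15 minus the mean index of the first event: 15 − 7.81 = 7.19, 15 − 7.62 = 7.38 and 15 − 7.05 = 7.95. This assumes the event is known before the next operation; fewer remain if it appears later.
3. An event delays someone only if it falls in one of the first 14 subjects, so the expected number of holds is 14q.

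| q | At least one of 15 | At least one of 10 | Two or more of 15 | Mean still waiting (of 15) | Expected holds |
|---|---|---|---|---|---|
| 1% | 14.0% | 9.6% | 1.0% | 7.2 | 0.14 |
| 2% | 26.1% | 18.3% | 3.5% | 7.4 | 0.28 |
| 5% | 53.7% | 40.1% | 17.1% | 8.0 | 0.70 |

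4. Further implantations if the HSC learned of the event only at continuing review. With accrual a, interval T and the event uniform within the interval, the uncapped mean is aT/2: from 3 × 0.5 / 2 = 0.75 to 8 × 1 / 2 = 4.0. That ignores the limit of 15. With r subjects remaining, the mean is aT/2 if r ≥ aT, and r − r²/(2aT) otherwise. Averaged over the first-event distribution in step 2, the range becomes about 0.7 (3 per year, 6 months) to 3.2–3.4 (8 per year, 12 months). It is near zero if the 9.3 consultation is prompt.

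5. Expected delay from a hold is 14q × review weeks: from 0.14 × 2 = 0.28 to 0.70 × 8 = 5.6 weeks over the study.

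6. Review or stop? One event in 15 has an exact (Clopper-Pearson) 95% interval of 0.2% to 32%, and one in 5 has 0.5% to 72%. A single event says too little about the true rate to justify an automatic stop, but it does justify a review.

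**The case against.** The best case for the plan is that oversight exists and a stop is possible. Safety is reviewed monthly, staff meet biweekly or monthly, the investigator may stop the study, the HSC is told of unexpected deaths within 24 hours, and the FDA is to be telephoned about fatal or life-threatening reactions with no condition on expectedness. A reader might infer from 14.2 that the study has no safety oversight; the documents do not support that. What stands is narrower: all of this is reporting, consultation or discretion, and none of it obliges implantation to wait.

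A reader might also infer that a related death or permanent disability judged expected need only appear in the continuing-review summary. That cannot be established here. Expectedness is judged against the protocol, consent form and brochure. The supplied protocol text names neither outcome as a risk, and the other two were not seen. Section 9.2 also opens with a sentence covering any serious adverse event, and the 9.3 consultation has no exception for expected events. All that can be said is that, if such an event were judged expected, the summary is the only route with a stated time.

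Nor do the replacement provisions add a separate defect. A replacement is simply the next implantation, an injured subject stays in unless they choose to leave, and reading 7.7 to cover a death is strained. That no review precedes replacement rests on silence, not on a rule against it.

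**Conclusion.** The point holds for the supplied text: there are no discontinuation criteria, and no required pause for HSC review after a related death or permanent disability. Sections 11 and 13 could contain such a rule and were not available.

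The size rests wholly on assumed rates. A trigger in a study of 15 is plausible, at 14% to 54% for risks of 1% to 5%, with about half the subjects still to be implanted when it occurs. The 0.7 to 3.4 further implantations apply only if the HSC hears nothing before continuing review, which cannot be verified. No reduction in subjects harmed is claimed, because that depends on what the HSC decides. This is a cheap improvement to subject protection; it does not show that the plan is unsafe as run.

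**What to change.** Replace the quoted sentence in 14.2 with:

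> After any death, or any event leading to irreversible or permanent disability (as in 9.3) or judged likely to do so, that is related or possibly related to the device or operation under the 9.1 causality rule, whether expected or not, no new or replacement implantation takes place until the HSC has reviewed the event and agreed that implantation may resume. The hold starts when the PI becomes aware of the event, which is reported to the HSC within 24 hours for a death and 7 days otherwise. FDA reporting under 9.2 is unchanged, and follow-up of implanted subjects continues.

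Using the 9.3 disability wording avoids a new undefined term. Including events judged likely to be permanent prevents the hold from waiting until permanence is confirmed at a later visit. Because the rule covers replacements, sections 5.2, 7.7, 9.3 and 14.1 need no cross-references.

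The cost is one paragraph, using the existing committee and existing reporting times. The downside is delay for waiting candidates: 0.3 to 5.6 weeks in expectation over the study, averaged over studies with and without an event. Any single hold would last the full review, assumed here to be 2 to 8 weeks.
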